1.0, 23-May-2022	Not Applicable, New Document	
2.0, 26-Aug-2022	 Clinical Investigation Plan Version removed from title page Format updates throughout Following sections updated per Protocol Version C: Section 3.1: Background Section 5: Investigational Plan – Study Design (Section Title also updated) Section 6: Determination of Sample Size Section 7: Statistical Methods:	
3.0, 20-Sep-2023	 Local Sponsor updated in title page: Removed Europe, added Australia Format and syntax updates throughout Superscripts added throughout, as applicable, to associated citations Following sections updated per Protocol Version D and Australia Local Requirements: Section 3.1: Removed Europe; Specified 780G pump is commercial in Canada and Australia Section 4: Updated "efficacy" to "effectiveness" Section 5:	

[figure not shown]
Page 4 of 25

Version	Summary of Changes	Author(s)/Title
4.0, 17-Jun-2024	 Following sections updated per Protocol Version E: Add Protocol version to cover page Section 3.1: Background Section 5: Investigational Plan – Study Design Section 7.4: Added imputation method for Visit 11 and Visit 13 Section 7.9.5.2: Updated method of generating pseudo-site data Section 7.9.6: Add subgroup analysis by age group 	

List of Abbreviations and Definitions of Terms 2.

Abbreviations			
AHCL Advanced Hybrid Closed Loop			
AUC	Area Under Curve		
BG	Blood Glucose		
BMI	Body Mass Index		
CGM	Continuous Glucose Monitoring		
CIP	Clinical Investigation Plan		
DD	Device Deficiency		
DKA	Diabetic Ketoacidosis		
DMC	Data Monitoring Committee		
eCRF	Electronic Case Report Form		
EOS	End of Study		
FDA	Food and Drug Administration		
HbA1c	Glycosylated hemoglobin		
IB	Investigator's Brochure		
ICF	Informed Consent Form		
ID	Identification		
ISO	International Organization for Standardization		
ITT	Intention to Treat		
NGSP	National Glycohemoglobin Standardization Program		
PP	Per Protocol		
SADE	Serious Adverse Device Effect		
SAE	Serious Adverse Event		
SAP	Sensor Augmented Pump		
SAP	Statistical Analysis Plan		
SG	Sensor Glucose		
SMBG	Self-Monitoring of Blood Glucose		
TDD	Total Daily Dose		
TIR	Time in Range		
UADE	Unanticipated Adverse Device Effect		
USADE	Unanticipated Serious Adverse Device Effect		

17-JUN-2024 Revision 4.0 Page 5 of 25

Introduction 3.

3.1 Background

In patients with insulin dependent diabetes mellitus, glycemic control is influenced by numerous factors such as insulin dosage, insulin absorption, timing, physiological/ lifestyle factors such as exercise, food intake, hormones and illness. These factors may contribute to significant variability in insulin requirements, which makes self-management of type 1 diabetes challenging.

Patients who are using continuous glucose monitoring (CGM), including sensor-augmented pump therapy, experience improvements in glycemic control. Advanced sensor-augmented insulin pumps are now being used in clinical practice including closed loop systems that automatically adjust the amount of insulin delivered to maintain glucose levels near the target value set by the user.¹

The MiniMed 780G system is a closed loop insulin system. In addition to automatically adjusting the amount of insulin delivered based on sensor glucose (SG) readings while operating in the SmartGuard feature, the MiniMed 780G insulin pump can also automatically deliver correction boluses when the system has been delivering at the maximum allowable basal rate and SG remains elevated. This pump is currently in commercial distribution in Canada, Australia, and the United States. Previous clinical investigations involved the 670G Version 4.0 pump (contains the 780G AHCL algorithm) used in combination with the Guardian Sensor (3) glucose sensor, Guardian Link 3 transmitter, Humalog and Novolog insulin. This investigation is intended to confirm safety and effectiveness of the 780G insulin pump used in combination with Fiasp insulin. Additional details for non-clinical/clinical testing are provided in the report of prior investigations/ Investigator's Brochure (IB).

3.2 **Purpose**

The purpose of this study is to evaluate the safety and effectiveness of the MiniMed 780G system in type 1 adult and pediatric subjects utilizing Fiasp (insulin aspart injection) in a home setting.

Study Objectives 4.

The objective of this study is to evaluate the safety and effectiveness of the MiniMed 780G system utilizing insulin Fiasp (insulin aspart injection) to support product and system labeling.

[figure not shown]
Investigational Plan - Study Design 5.

This global study is a multi-center, single arm study in insulin-requiring adult and pediatric subjects with type 1 diabetes on the MiniMed 780G system using Fiasp insulin as well as Medtronic Extended infusion set and reservoir. The run-in period and study period will be approximately 120 days long.

The period from Visit 1 (consent and screening) through Visit 6 should be completed in 30 days.

Companions:

17-JUN-2024 Revision 4.0 Page 6 of 25

Subjects will be required to have a companion who resides (or will live) in the same building (or home) during the study at night, and also to be physically present in the same building, home or location (if not at home) during the exercise and meal challenges. A companion should be present during meal challenges and for 4 hours following the start of the meal. Companions should be able to check SMBG, give glucose and/or administer glucagon.

Run-in Period (Visits 2-6):

The run-in period begins at Visit 2 and ends once Visit 7 occurs.

The intent of the run-in period will be to allow subjects to become familiar with new study devices while using their own insulin, either Humalog™ (insulin lispro injection) or NovoLog®/NovoRapid® (insulin aspart solution for injection). During the run-in period, study subjects with prior Automated Insulin Delivery (AID) control algorithm experience will be using the study pump with the SmartGuard feature activated (Auto Correction must remain OFF). and Medtronic Extended infusion set and reservoir. Subjects who do not have prior AID algorithm experience will use the system in Manual Mode. Before and during run-in period meal challenges, SmartGuard must be turned OFF, as noted in Meal Challenge instructional materials.

Note for subjects who have prior experience with the Auto Mode feature in Medtronic pumps (670G/770G): The term "Auto Mode" has been replaced by the term "SmartGuard" in the 780G pump.

During the run-in period, a 120 mg/dL (6.7 mmol/L) Auto Basal target should be set. It is recommended that Active Insulin Time is set to 4 hours.

Note: The Auto Basal target setting and Active Insulin Time should be set as recommended above, unless there is a documented safety reason that would not permit these settings to be used.

[figure not shown]
All subjects and their parents/caregivers as well as companions will be trained on diabetes management principles, such as the treatment of hyperglycemia and hypoglycemia. In addition, there will be training regarding the need to have access to and how to use glucose and glucagon in case of hypoglycemia.

Parents/caregivers and companions will be instructed that they should be with the subject in the same residence or building overnight.

If the MiniMed Clinical app/MiniMed Mobile app and the CareLink Clinical app are being used, parents/caregivers will be instructed that subjects should be connected to CareLink via the appropriate Smartphone app for data uploading and push notifications for low or high blood sugar when they are apart, e.g., at school, other activities. Instructions on the appropriate operation of the apps will be provided.

For study purposes, subjects, companions, and parents/caregivers will be trained and/or instructed to perform self-monitoring of blood glucose (SMBG) if subjects are experiencing a severe hypoglycemic event, severe hyperglycemic event or diabetic ketoacidosis (DKA). Subjects and their parents/caregivers

17-JUN-2024 Revision 4.0 Page 7 of 25

as well as companions will also be instructed to check blood ketones using a ketone meter if the Accu-Chek Guide Link study meter reading is greater than 300 mg/dL (16.7 mmol/L).

As a precaution, subjects and their parents/caregivers will be told that they should keep their own insulin pump supplies in a safe place and to have back up supplies on hand (such as insulin and syringe, or insulin pen) in the event they are asked to revert back to their own therapy during the study or experience study pump issues (i.e., infusion set occlusion with high glucose).

Subjects and their parents/caregivers will be instructed to insert sensors only in the locations that are specified in the User Guide materials. Reminders will be given to subjects at each office visit. Information about sensor insertions will be collected on an electronic case report form (eCRF) in the study database, i.e., insertion location.

Subjects and their parents/caregivers will be trained on all parts of the device system. This training may include access to and use of digital online learning content. A training checklist for both subjects and parents/caregivers will be implemented and completed.

The completion of emergency response training, including the use of a ketone meter, will be documented for companions. Companions may be trained in person or remotely.

After completion of training on the study devices, subjects and their parents/caregivers may attend additional visits in the days immediately following the start of system use, as needed. They may also take advantage of having access to the digital learning content.

Study Period (Visits 7-15):

[figure not shown]
All subjects will use Fiasp for the remainder of the study and will continue using the study pump, with SmartGuard feature enabled (including Auto Correction), infusion set and reservoir for approximately 90 days during the study period.

Subjects should use the system with the SmartGuard feature turned on at all times with Fiasp. When prompted by the pump, subjects should take appropriate measures and follow directions on the pump to remain in or return to the SmartGuard feature. During times when subjects are not able to use the SmartGuard feature, they should use the system in Manual Mode (e.g., Suspend before low and Suspend on low).

During the first 3 weeks (between Visits 7 and 11) of the study period, a 120 mg/dL (6.7 mmol/L) Auto Basal target should be set. It is recommended that Active Insulin Time is initially set to 4 hours and then titrated towards 2-3 hours or at the investigator's discretion.

During the next 3 weeks (between Visits 11 and 13) of the study period, the Auto Basal target setting should be set to 100 mg/dL (5.5 mmol/L). Active Insulin Time is recommended to be set to 2-3 hours or at investigator's discretion.

17-JUN-2024 Page 8 of 25 Revision 4.0

During the remaining weeks of the study (any time after Visit 13) of the study period, the Auto Basal target as well as Active Insulin Time should be set to what is best for the individual subject, at investigator's discretion.

Note: The Auto Basal target setting and Active Insulin Time should be set as recommended above, unless there is a documented safety reason that would not permit these settings to be used.

After completion of training on the SmartGuard function, subjects and their parents/caregivers may attend additional visits in the days immediately following the start of SmartGuard use, as needed. They may also take advantage of having access to the digital learning content.

Staged Enrollment:

The enrollment of subjects 7-17 years of age will not move forward until 10 subjects 18 years or older have completed 30 days of the study period and the Data Monitoring Committee (DMC) has determined that it is safe for 7-17 year olds to be enrolled into the study.

SMBG recommendations for 780G system:

With the 780G system and the Guardian 4 CGM, calibration is not required. However, a calibration is optional and will occur any time a blood glucose (BG) is entered. Occasionally, subjects may receive a notification if the pump needs a BG to enter or stay in the SmartGuard feature. Subjects will be instructed to perform SMBG if their symptoms do not match the sensor glucose (SG) value (i.e., they develop symptoms of hypoglycemia or hyperglycemia, but the SG value does not correlate with their symptoms).

Meal and Exercise Challenges:

All subjects will be asked to participate in meal and exercise challenges during the run-in and study period.

[figure not shown]
- All challenges are at least 4 hours in duration, beginning from the time when the challenge meals or exercise are started.
- There should not be more than one meal challenge on a single day.
- Meal and exercise challenges should not be scheduled on the same day during the specified time periods.

For example: A study period regular sized or large sized meal challenge should not take place on the same day as an exercise challenge.

Subjects will be asked to check BG at the start of the meal/exercise, as well as 2 hours and 4 hours after the start of the meal/exercise and provide correction insulin as necessary.

Throughout the study, it is important for subjects to avoid additional meal/snack or exercise up to four hours after the start of the challenge. If additional meal/snack or exercise is needed within 4 hours after the start of the challenge, the subject will acknowledge that food intake or exercise occurred. Content

17-JUN-2024 Revision 4.0 Page 9 of 25

and timing of the meal and exercise, along with BG values, will be recorded on a log provided by the study team.

Meal challenges for all subjects (Run-in and Study period):

The following meal challenges are required during the run-in and study periods:

[figure not shown]
- Two meal challenges during the run-in period with subjects using the system in Manual Mode between Visits 5 and 7
 - Regular sized meal with missed meal bolus at lunch
 - Large sized meal at breakfast, lunch or dinner
- Two meal challenges during the study period with subjects using the system in SmartGuard, Auto Basal target set at 120 mg/dL (6.7 mmol/L) – between Visits 9 and 11 of study period
 - Regular sized meal with missed meal bolus at lunch
 - Large sized meal at breakfast, lunch or dinner
- Two meal challenges during the study period with subjects using the system in SmartGuard, Auto Basal target set at 100 mg/dL (5.5 mmol/L) - between Visits 12 and 13 of study period
 - Regular sized meal with missed meal bolus at lunch
 - Large sized meal at breakfast, lunch or dinner
- One meal challenge during the study period with subjects using the system in SmartGuard, Auto Basal target set at currently set Auto Basal target – at any time after Visit 13 of study period
 - Large sized meal at breakfast, lunch or dinner

Meal challenges should only start if the following conditions are met:

- SMBG at start of meal is < 200 mg/dL (11.1 mmol/L)
- Sensor glucose is available.

Timing	Settings/Conditions	Meal Size	Meal Type	Notes
Run-in Period between visits 5 and 7	Manual Mode only Missed meal bolus	Regular sized meal	Lunch	Meal content, meal size and time of meal consumption should be established so that regular sized meal challenges during the study period can be matched
Run-in Period between visits 5 and 7	Manual Mode only	Large sized meal	Breakfast Lunch or Dinner	Meal content, meal size and time of meal consumption should be established so that large sized meal challenges during the study period can be matched
Study Period, between Visits 9 and 11	SmartGuard (120 mg/dL [6.7 mmol/L] setpoint) Missed Meal bolus	Regular sized meal	Lunch	Meal content, meal size and time of meal consumption should match regular meal taken during run-in and the regular meal taken at the 100 mg/dL (5.5 mmol/L) setpoint
Study Period, between Visits 9 and 11	SmartGuard (120 mg/dL [6.7 mmol/L] setpoint)	Large sized meal	Breakfast, Lunch or Dinner	Meal content, meal size and time of meal consumption should match meal at Setpoint of 100 mg/dL (5.5 mmol/L) and run-in period meal
Study Period,	SmartGuard	Regular	Lunch	Meal content, meal size and time of

17-JUN-2024 Revision 4.0 Page 10 of 25

between Visits 12 and 13	(100 mg/dL [5.5 mmol/L] setpoint) Missed meal bolus	sized meal		meal consumption should match regular meal taken during run-in and the regular meal taken at the 120 mg/dL (6.7 mmol/L).
Study Period, between Visits 12 and 13	SmartGuard (100 mg/dL [5.5 mmol/L] setpoint)	Large sized meal	Breakfast Lunch or Dinner	Meal content, meal size and time of meal consumption should match meal at Setpoint of 120 mg/dL (6.7 mmol/L) and run-in period large sized meal
Study Period Any time after Visit 13	SmartGuard (with current Auto Basal target setpoint)	Large sized meal	Breakfast Lunch or Dinner	Meal content, meal size and time of meal consumption should match large meal at Setpoint of 120 mg/dL (6.7 mmol/L)/100 mg/dL (5.5 mmol/L) and run-in period large sized meals

Regular Sized Meal Challenge with Missed Meal Bolus:

Between Visits 5 and 7 for the run-in period, while subjects are in Manual Mode with CGM, they will be asked to consume a meal without administration of a Meal Bolus at lunch. The size of the meal should be equivalent to what subjects would normally eat at this mealtime.

During the study period, once at each Auto Basal setpoint (i.e. 120 mg/dL[6.7 mmol/L] and 100 mg/dL[5.5 mmol/L]), subjects will be asked to consume the same regular sized lunch meal that they had during the run-in period. For example, if the regular sized meal was consumed without an insulin bolus for the meal at 12 pm during the run-in period, that same regular sized meal should be consumed at approximately the same time of day at each setpoint during the study period.

Large sized Meal Challenges:

On large sized meal challenge days, subjects will be instructed to eat at least 1 meal with at least 50% higher caloric intake including 50% more carbohydrates and 50% higher in fat. It is recommended that subjects eat food at restaurants or consume prepared meals. The FoodPrint™ phone app (as well as questions that will be asked by the investigational center staff during visits following meal challenges) will be used to collect information about type of food, name of restaurant (if applicable), subject confirmation that the meal eaten was different from any meal eaten within the last month and subject confirmation that meal size was at least 50% more than when subjects usually consume in terms of calories, carbohydrates and fat. The timing of the meal challenges will be at the investigator's discretion. The subject's parent/caregiver should be physically present in the same building, home or location (if not at home) during the meal challenge (and for 4 hours following the start of the meal), must be able to check SMBG (in case it is needed), and give glucose/administer glucagon as needed.

Exercise Challenge for all subjects (Study Period only):

The following exercise challenges are required during the study period:

2 exercise challenges at setpoint of 120 mg/dL (6.7 mmol/L, between Visits 9 and 11 of the study period)

17-JUN-2024 Page 11 of 25 Revision 4.0

- 2 exercise challenges at setpoint of 100 mg/dL (5.5 mmol/L, between Visits 12 and 13 of the study period)
- 1 exercise challenge at currently set Auto Basal target, at any time after Visit 13 of the study period

Conditions at start of the exercise challenges:

- SG should be present at the start of each exercise challenge
- The investigator or his/her staff will determine the minimum BG for each subject at the start of each exercise challenge. It will be noted on the subject's exercise log.

Timing	Settings/Conditions	Exercise duration	Notes
Study Period, between Visits 9 and 11	SmartGuard (120 mg/dL [6.7 mmol/L] setpoint)	Min 30 minutes, up to 1.5 hours	Challenge must take place on days without meal challenge
Study Period, between Visits 9 and 11	SmartGuard (120 mg/dL [6.7 mmol/L] setpoint)	Min 30 minutes, up to 1.5 hours	Challenge must take place on days without meal challenge
Study Period, between Visits 12 and 13	SmartGuard (100 mg/dL [5.5 mmol/L] setpoint)	Min 30 minutes, up to 1.5 hours	Challenge must take place on days without meal challenge
Study Period, between Visits 12 and 13	SmartGuard (100 mg/dL [5.5 mmol/L] setpoint)	Min 30 minutes, up to 1.5 hours	Challenge must take place on days without meal challenge
Study Period Any time after Visit 13	SmartGuard (with current Auto Basal target setpoint)	Min 30 minutes, up to 1.5 hours	Challenge must take place on days without meal challenge

Exercise Challenges Details:

To fulfill the exercise challenge requirement, subjects will be asked to engage in 0.5 up to 1.5 hours of physical exercise. During this time, subjects should use either the Auto Basal setpoint target of 100 mg/dL (5.5 mmol/L) or 120 mg/dL (6.7 mmol/L) (depending on what is required at that time of the study period) unless a subject prefers to use the 150 mg/dL (8.3 mmol/L) target before, during and immediately after the exercise challenges. The FoodPrint[™] phone app (as well as questions that will be asked by the investigational center staff during visits following exercise challenges) will be used to collect information about exercise type, date, time (start and finish of exercise), duration and name of the parents/caregivers/ companion present. The timing of the exercise challenge will be at the investigator's discretion. A photograph should be taken on each day of the exercise challenges to indicate where the exercise took place. Subjects may also use a Smartphone app to document their exercise. The subject's parents/caregivers/companion must be physically present in the same building, home or location (if not at home) during the exercise challenge, must be able to check SMBG (in case it is needed) and give glucose/administer glucagon as needed. Examples of types of exercise include, but are not limited to:

Revision 4.0 Page 12 of 25

- Running
- Cycling

17-JUN-2024

- Swimming
- Hiking
- Walking
- Games (e.g. Wii interactive video games)
- Indoor/outdoor playground (Pediatric subjects)
- Yoga/stretching
- Any sport activity that involves ongoing physical movement (e.g., tennis, golf, basketball, volleyball, soccer)
- Dancing
- Zumba
- Aerobics
- Spinning

Determination of Sample Size 6.

6.1 Sample Size and Investigational Centers

A total of up to 250 subjects with insulin-requiring type 1 diabetes age 7-80 will be enrolled at up to 25 investigational centers across the United States, Canada, and Australia in order to have 200 subjects enter the study period. Up to 125 subjects will be enrolled in the pediatric age group (7-17 years of age), up to 125 in the adult age group (18 years or older):

[figure not shown]
Subject Age Group	Sub-groups	Enrollment Goal (N)
D 1: 1 :	All Pediatric	Minimum 100 Subjects
Pediatric Age 7 – 17 years	Age 7 - 13 years	Minimum 20 Subjects
	Age 14 - 17 years	Minimum 20 Subjects
Adult Age 18 - 80 years	N/A	Minimum 100 Subjects

A minimum of 10 subjects and a maximum of 40 subjects is targeted for enrollment at each investigational center to ensure that the results from the individual investigational center may be pooled for analysis.

Investigational centers will be encouraged to enroll a study population that represents a wide variety of backgrounds.

Statistical Methods 7.

7.1 Study Subjects

7.1.1 General Aspects of Analysis

All data collected from the time of screening until the end of the study will be collected on eCRFs, subject questionnaires, and electronically by uploading the various devices. Data and analysis will be summarized in a Clinical Study Report. Any deviations from original statistical plan and the rationale will be described in the Clinical Study Report.

Disposition of Subjects 7.1.2

17-JUN-2024 Revision 4.0 Page 15 of 25

The number of subjects enrolled, completed, and early terminated in the study will be presented. The reasons for discontinuing prior to study completion will be summarized.

7.1.3 **Clinical Investigation Plan (CIP) Deviations**

All protocol deviations will be presented in the listings.

7.1.4 **Analysis Sets**

- Intention to Treat (ITT) Population
 - The ITT population will include all subjects who start the study. Primary safety, primary effectiveness, secondary effectiveness and descriptive endpoints will be evaluated for ITT population.
- Per Protocol (PP) Population
- The PP population will include all subjects who complete the study period, are in Auto Mode ≥ 80% of the time and without any major deviations. Primary safety, primary effectiveness and secondary effectiveness endpoints will be evaluated for PP population as the sensitivity/supplementary analyses.
- Safety Population

The Safety Population will include all enrolled subjects (subjects who signed Informed Consent Form (ICF)). Safety adverse events data summary will be evaluated for safety population.

[figure not shown]

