6.8 Insulin

Fiasp (insulin aspart injection) is a fast-acting insulin with the same active ingredient as Novolog/NovoRapid, used to treat adults and pediatrics with diabetes for the control of high blood sugar.

Subjects will use their own rapid-acting analogue insulin (Novolog/NovoRapid or Humalog) during the run-in period. During the study period, subjects will be provided with Fiasp for use.

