8.2 Subject Enrollment

D00459338

Subjects will be considered enrolled in the study upon signing the ICF and assent form (if applicable). A subject will be assigned a unique study subject ID via the eCRF, which is a 9-digit code (336XXXXX). The first three digits refer to the CIP number (336), the next three characters refer to the investigational center identifier, and the last 3 digits refer to the subject number assigned during Visit 1 (e.g., 336002001 is subject 001 from investigational center 002).

The investigator will maintain a log of all subjects enrolled in the clinical study, assigning a subject ID linked to their names, and alternative subject ID.

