9.1.1 Study Visit Schedule & Scheduled Follow-Up Visit Windows

Visit 1 to Visit 6 should be completed in 30 days.

• Visit 1 (Office): Consent and screening

Run-In:

- Visit 2 (Office/Virtual Office): Start Run-In
 - Eligibility has been confirmed
 - Start study pump and CGM
 - Register and upload study pump in CareLink Personal and CareLink system
- Visit 3 (Phone): Day 1 after Visit 2 Required for subjects without CGM or closed loop experience; as needed for all others

D00459338	Version E	Page 66 of 159	Medtronic
D00459556	version E	Page 66 01 159	meanorme

- Ask subjects and their parents/caregivers if they require assistance, e.g., additional training
- Ask subjects about adverse events and device performance
- Review CareLink reports
- Visit 4 (Phone): Day 3 after Visit 2 Required for subjects without CGM or closed loop experience; as needed for all others
 - Ask subjects and their parents/caregivers if they require assistance, e.g., additional training
 - Ask subjects about adverse events and device performance
 - Review CareLink reports
- Visit 5 (Phone): Day 7 (±2 days) after Visit 2
 - Ask subjects and their parents/caregivers if they require assistance, e.g., additional training
 - Ask subjects about adverse events and device performance
 - Review CareLink reports
 - o Remind subjects about run-in period meal challenge
- Visit 6 (Office/Virtual Office): Day 14 (±3 days) after Visit 2
 - Ask subjects about adverse events and device performance
 - Review CareLink reports
 - Visit 6 and 7 may be combined

Study Period:

- Visit 7 (Office/Virtual Office): Start Study Period, Day 7 (-7 days) after Visit 6
 - o Ask subjects about adverse events and device performance
 - Review CareLink reports
 - Start Auto Basal target at 120 mg/dL (6.7 mmol/L) setpoint with Active Insulin Time set to 4 hours, titrate towards 2-3 hours or at investigator's discretion
 - Turn on SmartGuard with Auto Corrections "ON"
 - Instruct subjects about the required meal and exercise challenges for both the 100 mg/dL (5.5 mmol/L) and 120 md/dL (6.7 mmol/L) setpoint between Visits 9 and 13 of the study period

CIP336 Clinical Investigation Plan A D00459338 Version E Page 67 of 159 Medtronic

- Visit 8 (Phone): Day 2 after Visit 7 Required for subjects without CGM or closed loop experience; as needed for all others
 - Adjust pump settings as needed
 - Ask subjects and their parents/caregivers if they require assistance, e.g., additional training

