11.1 Adverse Events

Throughout the course of the study, investigational centers will make all efforts to remain alert to possible reportable adverse events (AEs) or untoward findings. The study personnel will elicit reports of AEs from the subject at each visit (including phone calls) starting at the time of signing the informed consent documenting the medical diagnosis, date of event start and end, causality (relationship to device or procedure), treatment, outcome, assessment of seriousness, and description that includes the details of the event.

D00459338

Version E

Page 104 of 159

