7.2 General Methodology

Summary statistics for continuous variables will be represented by number of subjects(n), mean, median, standard deviation and categorical variables will be represented by counts and percentages. P-values for hypothesis testing will be evaluated based on one-sided testing using significance level of 0.025. Confidence intervals if needed will be reported as two-sided 95% confidence intervals. For primary safety, primary effectiveness and secondary effectiveness endpoints, normality will be verified for appropriate statistical methodology. Comparisons between the outcomes in study period and the threshold will be performed using one sample T-test for testing the statistical significance of the difference if normality assumption is met or Wilcoxon signed rank test if normality assumption is not met. In addition, the mean, median, min, and max will be presented when the normality assumption is not met.

The templates for Tables, Listings and Figures (TLFs) will be available in the TLFs document.

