7.10 Safety Evaluation

The safety of the study will be evaluated and summarized per all enrolled subjects, including but not limited to the following:

- Serious Adverse Events (SAE)
- Serious Adverse Device Effects (SADE)
- Unanticipated Adverse Device Effects
- Unanticipated Serious Adverse Device Effect
- Incidence of Severe Hypoglycemia
- Incidence of Severe Hyperglycemia
- Incidence of DKA

[figure not shown]

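### Adverse events are summarised over everyone who signed consent, so the summaries do not give the incidence of key events on Fiasp, which starts only at Visit 7

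*SAP*

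**What the plan says.** SAP 7.1.4 (Analysis Sets) defines the set and assigns the adverse-event summary to it: "The Safety Population will include all enrolled subjects (subjects who signed Informed Consent Form (ICF" (closing brackets omitted). SAP 7.10 repeats the rule: "The safety of the study will be evaluated and summarized per all enrolled subjects". SAP 7.9.7 and 7.10 both list SAEs, SADEs, unanticipated device effects, severe hypoglycemia, severe hyperglycemia and DKA. Neither gives an onset window.

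Enrollment comes well before Fiasp. Protocol 8.2 says: "Subjects will be considered enrolled in the study upon signing the ICF and assent form". Eligibility is confirmed at Visit 2, where Protocol 9.1.1 has the entry "Start study pump and CGM". The run-in uses the subject's own Humalog or NovoLog/NovoRapid. On Fiasp, Protocol 6.8 says: "During the study period, subjects will be provided with Fiasp for use". Protocol Table 5 first dispenses it at Visit 7.

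The nearest alternative set is ITT: "The ITT population will include all subjects who start the study". Starting the study is not tied to a visit, and 7.1.4 gives ITT to the primary, secondary and descriptive endpoints rather than to the adverse-event summary.

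For presentation, SAP 7.2 says that "categorical variables will be represented by counts and percentages". Protocol 11.1 has staff elicit events from the signing of consent, "documenting the medical diagnosis, date of event start and end, causality (relationship to device or procedure".

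**The concern.** This is a single-arm study meant to support labeling of the 780G system with Fiasp. Its primary safety endpoint is the change in HbA1c, which does not count severe hypoglycemia, severe hyperglycemia or DKA. The descriptive summaries are therefore the direct evidence on those events, with no control arm against which a denominator choice would cancel.

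Followed as written, the rule does two things:

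- It puts people who never received Fiasp into the denominator: screen failures after Visit 1 and dropouts between Visits 2 and 7.
- If the collection rule in Protocol 11.1 also serves as the counting rule, it adds run-in events on other insulins to the numerator.

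Two analysts following the same text could report different incidences, and neither figure would be the incidence on Fiasp.

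**Working it through.** **Inputs**

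- Enrolled: up to 250, planned so that 200 enter the study period (SAP 6.1). The cohort caps agree, 125 + 125 = 250, and so do the cohort minima, 100 + 100 = 200. No attrition rate is visible, so 1 − 200/250 = 20% is the implied figure, not a stated one.
- Run-in length d: Visit 6 is at day 14 ± 3 after Visit 2, and Visit 7 is 0 to 7 days later (Protocol 9.1.1). So d runs from 11 + 0 = 11 to 17 + 7 = 24 days.
- Study-period length D: Visit 15 is at day 90 (+7) after Visit 7, so 90 to 97 days.

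**If only study-period events are counted, as percentages.** The reported percentage is x/E and the percentage among Fiasp starters is x/S. The relative understatement is 1 − S/E. With E = 250:

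| Entering study period (S) | Understatement |
|---|---|
| 250 | 0% |
| 225 | 10% |
| 200 (target) | 20% |
| 190 | 24% |

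**If events are counted from the run-in onward.** Let k be the run-in daily event rate divided by the study-period daily rate, and R the number starting the run-in. With 200 entering, for infrequent events:

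reported ÷ Fiasp-period incidence = (k·R·d + 200·D) ÷ (E·D)

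- k = 1, low end (E = 250, R = 200, d = 11, D = 97): (2,200 + 19,400)/24,250 = 0.89.
- k = 1, high end (E = R = 200, d = 24, D = 90): (4,800 + 18,000)/18,000 = 1.27.
- Same settings, k = 0.5: 20,500/24,250 = 0.85 to 20,400/18,000 = 1.13.
- Same settings, k = 2: 23,800/24,250 = 0.98 to 27,600/18,000 = 1.53.

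The documents do not give k. At k = 1 a ratio above 1 reflects only longer follow-up. Screening days before Visit 2 are not in these ratios and would raise them if events in those days are counted.

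**Compared with sampling error.** Take 100 Fiasp starters in one cohort over 90 days: 100 × 90/365.25 = 24.64 patient-years. Apply the highest reference rates in Protocol Table 8, one event per subject, with denominators of 100 and 125. Intervals are exact two-sided 95%.

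| Event (rate per 100 patient-years) | Expected events | Over 100 | Over 125 |
|---|---|---|---|
| Severe hyperglycemia (71.64, under 15 years) | 17.7, say 18 | 18.0% (11.0 to 27.0) | 14.4% (8.8 to 21.8) |
| Severe hypoglycemia (20.9, a trial control arm, over 25 years) | 5.1, say 5 | 5.0% (1.6 to 11.3) | 4.0% (1.3 to 9.1) |
| DKA (9.9, registry, 25 years and under) | 2.4, say 2 | 2.0% (0.2 to 7.0) | 1.6% (0.2 to 5.7) |

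These rates are at the high end, and Protocol 12.2 itself urges caution with them. Even so, the intervals overlap heavily: the denominator effect is real but smaller than the sampling error.

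**The case against.** **The all-enrolled set is defensible.** It matches collection from consent and loses no event. This is a device study, causality is classified to device or procedure, and the study pump starts at Visit 2. That stands. For SADEs and unanticipated device effects, pump time before Visit 7 is valid exposure. The point is limited to SAEs, severe hypoglycemia, severe hyperglycemia and DKA on Fiasp, and it asks for an added summary rather than a replacement.

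**A reader might infer that the report will understate events by 20%.** The documents do not support that. It needs a study-period numerator over a consent-based denominator, and no visible SAP line sets that numerator. The protocol synopsis heads its endpoint block as covering the study period, but the safety endpoint visible there is HbA1c, and the heading is not repeated in SAP 7.9.7 or 7.10. Where only study-period events are counted, a reader given the number of starters could also recompute the percentage. Where run-in events are pooled, that is impossible without a split by onset.

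**A reader might subtract 90 days on Fiasp from 120 days of wear and take a 30-day run-in,** giving 120/90 = 1.33 at equal rates. Both figures are approximate in the protocol, and the visit windows allow at most 24 days.

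**A reader might infer that the plan nowhere provides a Fiasp-period summary.** That cannot be asserted. Part of the synopsis, the protocol's analysis-populations section and several SAP sections are not visible, and the table templates are a separate document.

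**The DMC already reviews events per 100 patient-years (Protocol 12.2).** True, but that is for monitoring. It does not set the denominator of the SAP summaries, and it is not stated as time on Fiasp.

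**Conclusion.** The point holds as a minor one. The stated rule in SAP 7.1.4 and 7.10 counts subjects who never receive Fiasp, and it leaves open whether run-in events on other insulins are included. The resulting figures are not the incidence of the listed clinical events on Fiasp.

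The size depends on the counting period. With study-period events only, percentages are understated by about 20% relative at the planned numbers. The 200 is a target, so the true figure follows attrition before Visit 7. With events counted from consent, the direction is unknown: about 0.89 to 1.27 at equal daily rates and 11 to 24 run-in days, before any screening time. Both calculations assume the planned totals, and the second also assumes a value for the run-in event rate.

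No hypothesis test or pass/fail result changes, because these summaries are descriptive. This is a cheap improvement in clarity, not a flaw in the study's conclusions.

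**What to change.** Keep the all-enrolled listing of events. In SAP 7.1.4, 7.9.7 and 7.10:

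1. State the period over which events are counted.
2. Add a set of subjects who start Fiasp at Visit 7. In that set, summarise SAEs, severe hypoglycemia, severe hyperglycemia and DKA with onset from Visit 7, by age cohort, both as subject proportions and as events per 100 patient-years of Fiasp exposure.
3. Report run-in events separately, over subjects who started the study pump at Visit 2, so that device effects across all pump exposure stay visible.

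If the table templates or sections not visible here already do this, cross-reference them in 7.1.4 and 7.10.

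The cost is some SAP wording and one table split. Event start and end dates are already collected, so no new data are needed. The downside for the sponsor is that some incidences may look slightly less favourable.
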